6.2.2. Safety Measures

Descriptive summaries of safety measures will be based on observed data only. No imputation of missing scores will be implemented.

6.2.3. Dates for Medical Events and Medications

Completely or partially missing onset and resolution dates of medical history (MH), AEs and concomitant medications (CM) will be imputed as follows:

Table 6: Handling of Missing Date for Medical Events and Medications

| Date | Type of Missing Date | Handling of Missing Date |
|---|--|--|
| Event onset date (e.g., YYYY-MM-DD) | Completely missing | No imputation will be applied. For AE, the event will be considered treatment-emergent. For CM, the event will be considered concomitant. For MH, the event will be considered to occur prior to Inform Consent date. |
| | Only YYYY is available | Use the first day of YYYY to impute the missing month and date parts of the onset date |
| | YYYY and MM are available, but DD is missing | Use the first day of MM to impute the missing date part of the onset date |
| Event resolution date (e.g., YYYY-MM-DD) | Completely missing | No imputation will be applied. The event will be considered ongoing (i.e., not resolved) at the last visit date. |
| | Only YYYY is available | Use the last day of YYYY to impute the missing month and date parts of the resolution date |
| | YYYY and MM are available, but DD is missing | Use the last day of MM to impute the missing date part of the resolution date |

Same rules will be followed to impute the completely or partially missing start and end dates of non-study medications.

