6.5. Discontinue Use of All IOP-lowering Medications

At the screening visit (Visit 1), subjects will be screened against the inclusion and exclusion criteria. Eligible subjects will be instructed to discontinue use of all IOP-lowering medications, if any, as follows (up to +7 days is allowed):

- Miotics: 7 days
- Oral/topical Carbonic Anhydrase Inhibitors (CAIs): 7 days
- Alpha agonists: 14 days
- Alpha/beta agonists: 14 days
- Alpha antagonists (α 1 blocker): 28 days
- Beta antagonists (β blocker, including $\alpha\beta$ blockers): 28 days
- Prostaglandins Analogs (PGA): 28 days
- Rho kinase (ROCK) inhibitor: 28 days
- Combination drugs: The longest washout period of the individual component will be used.

During the required washout period, subjects who discontinue their current treatment may, if the investigator deems necessary, be treated with a short-acting IOP lowering agent, topical CAI, e.g., brinzolamide or dorzolamide eye drops, one drop twice daily. Topical CAI treatment must be stopped 1 week before the randomization at Visit 2 (Baseline, Day 1). An interim safety visit during the washout period (mid-washout visit: Visit 1a) may be performed if, in the investigator's opinion, a subject's IOP may be of concern during the washout period. If subjects are treated with a topical CAI during the washout period, a mid-washout visit (Visit 1a) is recommended.

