8.2.2.1. Demographics, Medication/Therapy and Medical History

Demographics, Medication/Therapy and Medical History will be obtained through subject interviews at Visit 1 (Screening) to determine if the subject meets eligibility criteria.

Demographics

Demographics include age, sex, race, prostaglandin analogs naïve status, and ethnicity. They must be confirmed and recorded in the source documents.

Medical and Surgical History

Followings must be confirmed.

- Non-ocular medical history including diagnosis and relevant treatments within 5 years before the date of Visit 1
- All lifetime ocular medical history including diagnosis and relevant treatments
- All current ocular and systemic conditions

Following details must be recorded in the source documents.

- Diagnosis and treatment(s), affected eye(s) (if applicable), start date and resolved date.

Medications

Following must be confirmed.

- Prior medications that have been used for POAG or OHT within 28 days before the date of Visit 1 (Screening)
- All concomitant medications (including over-the-counter)

Following details must be recorded in the source documents.

- Name of medication, route of administration, treated eye(s) (if applicable), dose, frequency, indication, start date and stop date

Therapies

Following must be confirmed.

- Prior therapies that have been used for POAG or OHT within 28 days before the date of Visit 1 (Screening)
- All concomitant therapies

Following details must be recorded in the source documents.

- Name of therapy, treated eye(s) (if applicable), indication, start date and stop date

Surgical procedures occurring during the study

Following details must be recorded in the source documents.

- Name of surgical procedure, treated eye(s) (if applicable), indication, start date and stop date

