4.4. Other Definitions

4.4.1. Prior and Concomitant Medications

Non-study medications will be categorized into prior medications and concomitant medications. Specifically, the *prior medication* is defined as any non-study medication taken and ended prior to the treatment start date. The *concomitant medication* is defined as any non-study medication taken concurrently while on the study medication, i.e., the treatment period of a concomitant medication taken by a subject's needs to overlap with his/her treatment period of the study medication.

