6.2. Handling of Missing Data

6.2.1. Efficacy Measure

For subjects with the use of any non-study IOP lowering therapy to lower IOP, unless otherwise specified, the IOP data collected after the non-study IOP lowering therapy will be censored (treated as missing) in efficacy analyses.

For each IOP endpoint, no imputation is needed for the analysis on observed cases using the mixed-effects model for repeated measures (MMRM).

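### SAP Table 6 classes a medication with a completely missing start date as concomitant without checking its stop date, which contradicts SAP 4.4.1 (minor; descriptive medication outputs only)

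*SAP*

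**What the plan says.** SAP 6.2.3 (Table 6) sets the rules for incomplete dates. When the start date is completely missing, no date is imputed and the record is assigned a class directly: "For CM, the event will be considered concomitant". The row does not mention the stop date. When at least the year is known, a start date is imputed instead; for a year alone the rule is "Use the first day of YYYY to impute the missing month and date parts of the onset date". A closing sentence under the table widens the scope: "Same rules will be followed to impute the completely or partially missing start and end dates of non-study medications".

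SAP 4.4.1 defines the two classes. A prior medication "is defined as any non-study medication taken and ended prior to the treatment start date". For a concomitant one, "the treatment period of a concomitant medication taken by a subject's needs to overlap with his/her treatment period of the study medication". SAP 4.1.2 takes the treatment start date as the date of the first dose.

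SAP 7.5 tabulates and lists prior and concomitant medications separately for the Safety population. The SAP does not say whether 4.4.1 or Table 6 governs when they disagree.

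**The concern.** Under SAP 4.4.1, a recorded stop date before the first dose settles the class: the medication is prior, whenever it began. Table 6 overrides that known fact because a different date is missing.

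This trial's design can produce such records. Subjects on IOP-lowering drugs are told at Visit 1 to stop them (Protocol 8.1.1), with class-specific washouts of 7 to 28 days (Protocol 6.5, for example "Prostaglandins Analogs (PGA): 28 days"). Washout is confirmed at Visit 2 (Protocol 8.1.3), so the stop date should be known. If a date is missing, it is more likely to be the start of a long-standing drop.

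What is at stake is the accuracy of the medication tables and listings. Protocol 6.6.1 prohibits ocular medications during the study, apart from a short list of exceptions and the study drug. A washed-out drop shown as concomitant would look like use of a prohibited drug on treatment, in a subject who had in fact complied.

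**Working it through.** No figure in the plan bears on this point, so the check applies both rules to the same records.

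**Inputs**
- Table 6 (SAP 6.2.3): start completely missing → concomitant. Start partly known → impute the first day of the known year or month, then classify.
- SAP 4.4.1: prior if stop date < treatment start date; concomitant if use overlaps the study-treatment period.
- Protocol 6.5: a prostaglandin analog is stopped 28 days before baseline.
- Protocol 8.2.2.1: start and stop dates are both to be recorded for each medication.
- Illustration only, not from the documents: treatment start 1 March 2019. A stop 28 days earlier is 1 February 2019.

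**Results**

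| Start date recorded | Stop date | Table 6 as written | SAP 4.4.1 |
|---|---|---|---|
| 5 May 2015 | 1 Feb 2019 | prior | prior |
| May 2015 (imputed 1 May 2015) | 1 Feb 2019 | prior | prior |
| 2015 (imputed 1 Jan 2015) | 1 Feb 2019 | prior | prior |
| completely missing | 1 Feb 2019 | **concomitant** | **prior** |
| completely missing | 11 Mar 2019 (on treatment) | concomitant | not prior; in use up to a date within treatment |
| completely missing | missing | concomitant | cannot be decided from the definition |

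Only the fourth row conflicts. A start year alone is enough to remove the conflict. In the last two rows the Table 6 default is reasonable, because nothing known rules out overlap.

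**With the stop date checked first.** Row four becomes prior and every other row is unchanged. Imputed stop dates cause no difficulty. Table 6 imputes a partial stop date to the last day of the known month or year, and treats a completely missing one as ongoing. A medication is therefore moved to prior only if even the latest possible stop date precedes the first dose.

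**Where the class is used**
- SAP 7.5: yes, in the prior and concomitant tables and listings.
- SAP 6.2.1 (censoring): it refers to use of non-study IOP-lowering therapy, after which "the IOP data collected after the non-study IOP lowering therapy will be censored (treated as missing) in efficacy analyses". It does not refer to the concomitant class.
- SAP 5.4 (per-protocol set) and 7.4 (major deviations): both rest on study-team review of deviations, before unmasking and before database lock respectively. Neither refers to the class.

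**Count.** The number of affected records would be the number of medication records × the share with a completely missing start date × the share of those with a known stop before the first dose. The documents give none of these factors, so no number is calculated.

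**The case against.** The strongest reply is that the passages can be read together. The definition in SAP 4.4.1 needs only the stop date, so an analyst could apply it first and use Table 6 only where it cannot decide. Table 6 is introduced as covering medical history, adverse events and concomitant medications. Its closing sentence extends the rules for imputing dates, and for a completely missing start nothing is imputed. On that reading no record is misclassified. Part of this stands: the error is not certain, because a careful programmer could avoid it. But the SAP does not state that order. The row assigns concomitant status, which would be pointless for drugs already classed as concomitant, and the closing sentence names non-study medications generally.

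A second reply is that Protocol 9.3.5 asks for conservative imputation. That supports the default where overlap is uncertain. It does not support overriding a recorded stop date that excludes overlap.

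Three limits on the consequence stand in full. The trigger is narrow, since even the year must be missing. The outputs are descriptive and carry no test, and the history of pre-study drugs is fixed before randomization, so no difference between arms is to be expected. Prior prostaglandin use is also summarized separately as a baseline characteristic (SAP 7.2), so that information does not depend on these tables.

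A reader might infer more: that a false concomitant label would trigger the SAP 6.2.1 censoring, or a deviation leading to exclusion from the per-protocol set, and so remove valid Week 2 and Week 6 IOP. The documents do not support this. None of those rules uses the label, and the inference needs a programming choice that the SAP does not describe.

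**Conclusion.** The point holds as a minor inconsistency. Applied literally, Table 6 contradicts SAP 4.4.1 for a medication with a completely missing start date and a known stop date before the first dose. Each such record would be placed in the concomitant table and listing instead of the prior ones.

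This assumes that Table 6 is followed as written, without first applying 4.4.1, and that at least one such record occurs. How many will occur is unknown. The effect shown is confined to the descriptive outputs of SAP 7.5. No effect on IOP censoring, the per-protocol set or the primary analysis is demonstrated.

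**What to change.** In SAP Table 6, replace the sentence for medications in the row for a completely missing start date with: *For CM with a completely missing start date, the medication is concomitant unless its stop date (observed or imputed) is before the treatment start date, in which case it is prior.*

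This brings Table 6 into line with SAP 4.4.1 and keeps the conservative default wherever overlap cannot be excluded. It costs one sentence in the SAP and one condition in the analysis-dataset program, with no new data.

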9.3.5. Handling of Missing Values

In the analysis of IOP, subjects with missing IOP value at any timepoint at Week2 or Week6 may be imputed using the last-observation-carried-forward (LOCF) approach for sensitivity analyses.

For medical events including AEs, completely or partially missing onset and resolution dates will be imputed in a conservative fashion to be detailed in SAP. The same rules will be followed to impute completely or partially missing start and end dates of non-study medications.

Unless otherwise specified, descriptive summaries will be based on observed cases. Additional details on handling of missing data will be provided in the SAP.

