4.3. Safety-Related Definitions

4.3.1. Adverse Event

Under Protocol 011712IN, an AE is defined as any untoward medical occurrence (e.g., sign, symptom, disease, syndrome, intercurrent illness) that occurs in a study subject, regardless of the suspected cause and regardless of timing of study medication administration. An *on-study* AE can occur any time after the date of informed consent through the last study visit. An AE will be considered as *treatment-emergent* if the AE occurred on or after the treatment start date up to the 2 days after treatment end date. Treatment-emergent AEs are a subset of on-study AEs. Both on-study and treatment-emergent AEs will be recorded, but only treatment-emergent AEs will be tabulated.

The severity of each AE will be graded by the Clinical Investigator as Mild, Moderate, or Severe.

Each AE will be classified into a system organ class (SOC) and coded to a preferred term (PT) using Medical Dictionary for Regulatory Activities (MedDRA), version 21.1 published in 2018.

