6. GENERAL CONSIDERATIONS

All measures will be summarized by treatment (planned or actually received) descriptively. Continuous variables will be summarized using descriptive statistics such as number of observations (n), mean, standard deviation, median, minimum, and maximum. Categorical variables will be tabulated using frequency (n) and percent (%).

Analysis treatment groups are defined as DE-117 QD/Vehicle QD or DE-117 BID.

The statistical testing will be conducted at a significance level of 0.05 (2-sided) unless specified otherwise. No statistical testing will be conducted for safety measures.

All data manipulations, descriptive summaries, and statistical hypothesis testing will be performed using Statistical Analysis System (SAS) Version 9.4 or later.

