9.1. Adverse Event

Subjects with any AE(s), SAE(s), SAR(s) serious SAR(s) and significant AE (AE leading to study drug discontinuation) will be tabulated by type of AE(s) for each actual treatment received.

Besides the overall AE summary, subjects with any AE(s) and any SAR(s) will be tabulated by SOC and preferred term. A subject who experienced multiple AEs within a SOC or preferred term will be counted only once for that SOC or preferred term.

The same analysis above will be performed for ocular AEs and non-ocular AEs.

AEs, AEs leading to death, AEs leading to study drug discontinuation, SAEs, SARs and ESIs, if any, will be listed separately.

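### Partial AE onset dates are imputed without reference to first dose, so some on-treatment AEs leave the AE tables while wholly undated AEs stay in

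*SAP*

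**What the plan says.** The onset rows of SAP Table 6 (section 6.2.3) depend on how much of the date is known:

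- Day missing: "Use the first day of MM to impute the missing date part of the onset date".
- Only the year known: "Use the first day of YYYY to impute the missing month and date parts of the onset date".
- Nothing known: no date is imputed, and "For AE, the event will be considered treatment-emergent".

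Neither partial-date row mentions treatment start.

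SAP 4.3.1 calls an AE treatment-emergent "if the AE occurred on or after the treatment start date up to the 2 days after treatment end date", and adds that "only treatment-emergent AEs will be tabulated". Treatment start is the date of the first dose (SAP 4.1.2), taken on the evening of Visit 2, so it can be any day of the month.

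Protocol 9.3.5 sets the standard that Table 6 is meant to deliver: for AEs, "completely or partially missing onset and resolution dates will be imputed in a conservative fashion to be detailed in SAP".

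**The concern.** Taken together, these rules give an odd ordering. An AE with no onset date is tabulated. The same AE, once the site has recorded that it began in the month of first dose, is moved to the 1st of that month, falls before treatment start and disappears from the tables. Knowing more about the date removes the event.

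For treatment-emergence this is the opposite of conservative. AEs are collected from consent (Protocol 8.3.1), so the cut at first dose decides what is tabulated, and neither document has a tie-break for partial dates.

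The AE tables are the main display for the safety objective, BID compared with QD. Treatment lasts six weeks, and the loss falls mostly on events soon after first dose. With about 50 subjects per arm, one subject dropped from a row lowers that incidence by 1/50 = 2 percentage points.

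**Working it through.** **Example.** First dose is on 10 March.

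| True onset | Recorded as | Imputed | Tabulated? |
|---|---|---|---|
| 12 March | March, day missing | 1 March | No |
| 31 March | March, day missing | 1 March | No |
| 2 April | April, day missing | 1 April | Yes |
| 12 March | nothing | none | Yes |

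**Inputs.** The treatment-emergent window runs from Day 1 to Day 43 (nominal Visit 4) plus 2 days, which is 45 days (SAP 4.3.1 and Table 2). Screening lasts up to 35 days (SAP 3.1). The documents give no count of partial dates and no figure to reproduce.

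**Assumptions.** First dose is equally likely on each of 365 days, and true onset is equally likely on each day of the window.

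**Day missing, given start date.** For a first dose on day d ≥ 2 of a month with D days, every onset in the rest of that month is lost, so the share lost is (D − d + 1)/45. In a 31-day month:

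- start on the 2nd: 30/45 = 67%
- start on the 15th: 17/45 = 38%
- start on the 28th: 4/45 = 9%
- start on the 1st: 0%

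**Day missing, averaged over the year.** Summing D − d + 1 over d = 2 to D gives D(D − 1)/2 lost onset days per month. Over the year this is 7 × 465 + 4 × 435 + 378 = 5,373.

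- 45-day window: 5,373/(365 × 45) = 5,373/16,425 = 32.7%
- 43-day window, since AE collection normally stops at the exit visit: 5,373/15,695 = 34.2%

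**Early and late onsets.**

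- Days 1–14: each month contributes 105 + 14(D − 15) lost onset days, so 7 × 329 + 4 × 315 + 287 = 3,850. The share is 3,850/(365 × 14) = 3,850/5,110 = 75.3%.
- Days 15–45: (5,373 − 3,850)/(365 × 31) = 1,523/11,315 = 13.5%.

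**Year only.** The AE is kept only if first dose is on 1 January or onset falls in a later calendar year. Lost: 364 × 45 − (1 + 2 + … + 44) = 16,380 − 990 = 15,390, and 15,390/16,425 = 93.7%.

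**Pre-dose onsets, which matter for the fix.** An onset k days before first dose falls in the month of first dose when k ≤ d − 1.

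- Onsets spread evenly over 35 days: 5,373/(365 × 35) = 5,373/12,775 = 42.1%
- Over 28 days: 5,348/10,220 = 52.3%

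**The case against.** The strongest objection is about size. Every percentage is conditional on a partial onset date. With about 100 subjects, six weeks of treatment, AE queries at Day 15 and Day 43, prompt eCRF entry and source data verification, there may be very few such dates and almost no year-only ones. The lost events also remain visible: "AEs, AEs leading to death, AEs leading to study drug discontinuation, SAEs, SARs and ESIs, if any, will be listed separately". In addition, "No statistical testing will be conducted for safety measures", and the rule is the same in both arms. All of this stands, and it keeps the point well short of critical. Listings do not correct tabulated rates, however, and an identical rule need not have an identical effect if early AEs differ by dosing frequency.

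The 33% also assumes that a missing day is as likely for early as for late AEs. Recall before Visit 4 covers about 28 days, against about 14 before Visit 3, so missing days could be commoner later. On the 43-day window, if they are twice as likely after Day 14 the share lost is (3,850 + 2 × 1,523)/(5,110 + 2 × 10,585) = 6,896/26,280 = 26%. If four times as likely, it is 9,942/47,450 = 21%. The size changes but the mechanism does not.

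It can also be said that the rows of Table 6 cover different cases, and that earliest onset with latest resolution is conservative for duration. That is true, but SAP 9.1 plans no summary of AE duration. In that section the onset date matters because it decides tabulation.

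**Conclusion.** The concern holds. Followed exactly, the SAP misclassifies on-treatment AEs whose partial onset date falls in the month or year of first dose, and nothing else in either document recovers them for the tables. That follows from the text and needs no assumption.

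The size does rest on assumptions. With even start dates and onsets, about a third of day-missing on-treatment AEs are lost (0% to 67% by start date), and about a fifth to a quarter if missing days cluster late. The absolute number is unknown and probably small. No efficacy conclusion changes. It should be fixed before database lock because it departs from the protocol's own standard and is cheap to correct.

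**What to change.** Add a row to SAP Table 6, for AEs only. Impute onset as the treatment start date if all three conditions hold:

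1. The known year, or year and month, equals that of treatment start.
2. The resolution date is missing or is not before treatment start.
3. The AE was not already recorded at a visit before first dose (Visit 1a or Visit 2).

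Otherwise keep the first-of-month or first-of-year rule. Leave the row for completely missing dates as it is. Concomitant medications need no change, because SAP 4.4.1 separates prior from concomitant use by whether use ended before treatment start.

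A true on-treatment AE cannot fail condition 2 or 3. In the enumeration above, imputing to treatment start whenever condition 1 holds leaves 0 of 32,850 cases lost (16,425 for each type of partial date).

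The cost is SAP wording and a short programming step. Condition 3 is needed because 42% of day-missing pre-dose onsets over a 35-day screening period (52% over 28 days) fall in the month of first dose, and without it the unresolved ones would become treatment-emergent. AEs are queried at both pre-dose visits (Protocol 8.1.2 and 8.1.3), so the information should exist. The sponsor should confirm that the visit of first report can be recovered from the data.

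Some over-counting remains. Pre-dose AEs with partial dates that are first reported after dosing will be tabulated unless their resolution date rules them out. Table 6 also moves partial resolution dates to the end of the month or year, which weakens condition 2. Both errors are in the conservative direction.
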